4.1 To discuss each assessment in detail:Physical activity and function

4.1.1 Cardiopulmonary Exercise Test

Exercise capacity will be assessed using a symptom-limited Cardiopulmonary Exercise Test (CPET) on a motorized treadmill with expired gas analysis to determine VO_{2peak} , according to guidelines for clinical populations.⁸⁸ Every effort will be made by study staff to ensure that all patients who take beta-blockers will have taken their medication prior to testing. CPET will be administered +/- 2 hours from when patients would be participating in exercise training (see below). All CPET data will be recorded as the highest 30-second value elicited during the CPET. During exercise, heart rate and rhythm will be monitored continuously using a 12-lead ECG. The ECG will be used to make sure the subject does not have any abnormalities before, during, and after the treadmill stress test. This test will last approximately one hour. Additionally, the Patient-Reported Outcomes Measurement Information System (described below) Physical assessment will be completed.

To discuss patient study interventions in more detail:

Prior to beginning the exercise intervention, cardiopulmonary exercise testing (CPET) will be used to both determine the patient's baseline and determine safety and suitability of patient participation.

A Research Program Targeting Pre-, Peri-, and Post-transplant Optimization Program (R-POP)

Version 1.18: October 25, 2022

Page 11

Specifically, during exercise, heart rate and rhythm will be monitored continuously using a 12-lead ECG. The ECG will be used to make sure the subject does not have any abnormalities before, during, and after the treadmill stress test. Results will be reviewed by a physician before the subject is cleared to participate in interval training.

For the interval training intervention, patients will be asked to complete up to 3 x 30-minute structured high intensity interval training aerobic exercise sessions/week. The structured aerobic exercise will incorporate an intensity specific interval training design with intensities relative to each patient's individual fitness and thus comparable between patients. Heart rates and intensities will be determined from the maximal exercise test (CPET). The preferred mode will be walking, however if the patient prefers swimming or cycling we will adapt the plan accordingly. For the first session, patients will come to the Duke Center for Living for in person evaluation and training. Patients will be asked to wear a chest heart rate strap which will connect with the heart rate monitor. This will ensure accurate heart rate at higher intensity activities. Patients will also wear an Apple Watch and results of heart rate monitoring on the watch will be compared to the chest strap. Before and after each session patients will engage in an active 5-minute warm-up and cool-down at an intensity corresponding to 40%-50% VO_{2peak} . In our experience this is similar to a slow, leisurely walk. Following the warm-up, patients will increase speed to correspond with an intensity of approximately 80% VO_{2peak} for 1-minute before returning to warm-up speed for 1-minute (50% VO_{2peak}). In our experience this is similar to a brisk uphill walk, or climbing stairs. Patients will complete up to 10 of each vigorous intensity (80%) 1-minute interval and 10 of each low intensity (50%) 1-minute interval, or 30-minutes total exercise (including warm-up and cool-down). This type of training has been shown to be safe and feasible in breast and prostate cancer while improving fitness rapidly with little fatigue and few adverse events.⁸⁹ After the initial training session in person, a subsequent training session will take place at the patient's home via iPad/iPhone videoconference using a device provided to the patient to provide additional support and the opportunity to answer questions. Subsequent sessions will be done independently by patients, but study staff will be available via iPad/iPhone if questions arise.

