2.9 Summary

There is the potential to improve these areas during the 2-3 month window between new patient evaluation and HCT. Much of the literature has focused on improving health indicators during the transplant process to support better outcomes post-HCT. However, the question we want to answer is: can patients improve their health and function pre-HCT and, thus, improve outcomes post-HCT? We are aware of only one intervention taking a similar, but not identical approach.⁸¹ Uniquely, we will target patient participants at their initial evaluation, prior to hospital admission, and follow them throughout the transplant process to discharge, providing them with consistent, evidenced-based physical activity, diet, cognitive, social, and emotional interventions. Our hope is to improve patient outcomes and quality of life by intervening prior to HCT.

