3.0 PATIENT AND CAREGIVER ELIGIBILITY

3.1 Patient Inclusion criteria

- 1) Plan to undergo an allogeneic hematopoietic stem cell transplant for any cancer or non-cancer illness within the next 6 months
- 2) Age 18-80 years

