4.0 STUDY PROCEDURES AND ENDPOINTS

Those who consent to participate in R-POP will return within one month (preferably within two weeks) for a separate day of assessments (e.g. cardiopulmonary exercise testing), nutrition education (e.g. what constitutes a serving of protein), and training on how to use iOS devices (e.g. iPad, iPhone) and activity trackers (e.g. Apple Watch), which will be provided to patients for their use during the duration of study participation. In their 2011 report the World Health Organization states that, “the use of mobile and wireless technologies to support the achievement of health objectives (mHealth) has the potential to transform the face of health service delivery across the globe,”⁸² and this investigation will contribute to solidifying use of a mHealth platform with all Duke HCT patients. iPad or iPhones will be pre-loaded with apps and/or PDFs which may include (1) SplendoFit (2) Technology Recordings to better Understand BMT (TRU-BMT), developed by co-Is [name] and [name] to monitor patient reported outcomes of health, quality of life, and nutrition (Duke IRB Pro00068979), (3) an electronic copy of the Duke ABMT Patient Handbook (this is an electronic version of a paper handbook that is given to all transplant patients as part of standard of care), and (4) an electronic copy of Duke ABMT Recipes for Transplant Patients (this is an electronic copy of paper recipes available to all transplant patients as part of standard of care). (5) Jabber, or a similar program, to facilitate video communication (e.g. for monitoring and support of exercise sessions); (6) recipes for meals and smoothies for HCT prepared by collaborator [name] (registered dietitian).

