5.0 ANTICIPATED TOXICITIES

We do not anticipate any major toxicities occurring with participation in our investigation. The study interventions are evidenced-based and aimed at improving any health concerns the participants may have. To ensure the utmost safety of our participants going through exercise training (**as described above in section 4.1**) study staff will ensure that all patients who take beta-blockers will have taken their medication prior to training to avoid any blood pressure-related events.

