Skin Swab – risk of mild discomfort and irritation from skin swabbing, self-limited and will stop on request, minimal risk

Stool Collection – risk of mess with transferring stool sample from hat into collection container, minimal risk

Blood collection – care will be taken to prevent excess blood draw, minimal risk

Interval Training – While there are risks associated with any exercise activity, such as chest pain, shortness of breath, muscle cramping or discomfort, musculoskeletal injury, exacerbation of underlying coronary disease,

**A Research Program Targeting Pre-, Peri-, and Post-transplant Optimization Program
(R-POP)**

Version 1.18: October 25, 2022

Page 26

patient with a known history of at-risk coronary conditions will be excluded, as with patients with abnormal findings on CPET testing. To ensure the utmost safety of our participants going through exercise training, study staff will ensure that all patients who take beta-blockers will have taken their medication prior to training to avoid any blood pressure-related events. Furthermore, the first training session will be performed in a monitored setting by trained professionals; the second session (first session at home) will be performed over a monitored video link by trained professionals, which will also occur weekly the first month, monthly for the remainder of the study, and as needed or requested by study staff or subjects; subjects always have the option to return in person for additional sessions. Therefore, these risks will be mitigated by supervision and training and this intervention is deemed low risk.

Referral to psychology/psychiatry, if warranted – while there may be risks of patient psychological distress associated with this referral, the likelihood of benefit from seeing a psychologist/psychiatrist to someone with potential depression or PTSD is outweighed by the risks. There may be financial risks associated with psychology/psychiatry referrals depending on insurance. Low risk.

Additional referral to social work, if warranted – while there may be risks of patient psychological distress associated with this referral, the likelihood of benefit from seeing a social worker to someone with social support needs is outweighed by the risks. Low risk.

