Protections against risks associated with exercise are described above. To review: while there are risks associated with any exercise activity, such as chest pain, shortness of breath, muscle cramping or discomfort, musculoskeletal injury, exacerbation of underlying coronary disease, patients with a known history of at-risk coronary conditions will be excluded. Furthermore, cardiopulmonary exercise testing will be performed as an

A Research Program Targeting Pre-, Peri-, and Post-transplant Optimization Program (R-POP)

Version 1.18: October 25, 2022

additional precaution prior to allowing patients to participate in the exercise intervention. While CPET testing is an exercise itself and has risks, this activity will be performed in a monitored setting by trained professionals. To ensure the utmost safety of our participants going through exercise training, study staff will ensure that all patients who take beta-blockers will have taken their medication prior to training to avoid any blood pressure-related events. Similarly, subjects undergoing interval training will also continue to take their beta-blockers and other medications.

With regard to interval training, the first training session will be performed in a monitored setting by trained professionals; the second session (first session at home) will be performed over a monitored video link by trained professionals, which will also occur weekly the first month, monthly for the remainder of the study, and as needed or requested by study staff or subjects; subjects always have the option to return in person for additional sessions. Therefore, these risks will be mitigated by supervision and training and this intervention is deemed low risk.

Plans for ensuring necessary medical or professional intervention in the event of adverse effects on participants

Initial assessments will take place in person with trained medical staff available to respond either immediately (e.g. CPET testing, interval training) or within 24 hours (e.g. psychological distress brought up by questionnaires/surveys). While adverse events may arise after patients return home, study staff will be available 24 hours a day, seven days a week, to respond to patient concerns and direct them to appropriate care. In fact, the TRU-BMT app and SplendoFit app both contain a tab for contact information and who to call at what time.

Plans for handling incidental findings

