Incidental findings related to cardiopulmonary concerns (e.g. CPET testing or interval training) would lead to notification of the primary provider and referral to cardiology or other appropriate services.

Incidental findings related to nutritional status are part of the goal of this study and, the primary provider will be notified.

Incidental findings related to psychological distress, depression, lack of social support, etc. (e.g. raised by questionnaires/surveys) would lead to notification of the primary provider and referral to psychology, psychiatry, social work, or other appropriate services.

Incidental findings related to cognitive function (e.g. raised by questionnaires/surveys) would lead to notification of the primary provider and referral to neuropsychology, occupational therapy, or other appropriate services.

c. Vulnerable Subjects

As this study is built around the Duke Adult Bone Marrow Transplant Program, which only treats patients age 18 and older, fetuses, neonates, and children will be excluded. While subjects may be as old as 80 years, adults with cognitive impairment and unable to consent to participation will not be enrolled. Pregnant women are excluded from transplant and will therefore be excluded from this study. Prisoners and institutionalized individuals are also excluded from this study.

Potential Benefits of the Proposed Research to Research Participants and Others

Potential benefits to research participants

A Research Program Targeting Pre-, Peri-, and Post-transplant Optimization Program (R-POP)

Version 1.18: October 25, 2022

Studies have shown that patients with poor function (e.g. depression, physical frailty) prior to transplant have worse outcomes after transplant (e.g. increased treatment-related mortality). By addressing these functional domains during the pre-transplant period (median 101 days), we have the opportunity to both improve function as well as patient outcomes.

In addition, this study may identify issues pertaining to caregiver distress, leading to the development of further studies targeted at caregivers.

Why the risks to subjects are reasonable in relation to the anticipated benefits

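### Section 4.1.1 makes all home interval training after the second session independent, while Section 7 requires weekly, then monthly, monitored video and counts it among the safeguards behind the low-risk rating

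*Combined protocol and SAP*

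**What the plan says.** **Section 4.1.1** is the text that tells staff how to deliver the training. Patients are asked for up to three 30-minute sessions a week, with one-minute efforts at about 80% VO2peak. Session 1 is in person and a second session is at home by videoconference. After that: "Subsequent sessions will be done independently by patients, but study staff will be available via iPad/iPhone if questions arise". No further video is scheduled and there is no pointer to Section 7.

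**Section 7.0** covers the same training twice, in the list of risks (Interval Training) and again under protections against risk. Both places put the first home session over a monitored video link run by trained professionals, "which will also occur weekly the first month, monthly for the remainder of the study", with more if staff or patients ask. Both then conclude that "these risks will be mitigated by supervision and training and this intervention is deemed low risk".

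**Section 5.0**, on toxicities, points the reader to the training "as described above in section 4.1", not to Section 7.

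**Section 4.0** lists a video-call program on the loaned device and gives exercise monitoring as an example of its use. It also describes real-time tracker data that staff can act on. It sets no video frequency.

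**The concern.** A safety procedure has two different rules in one protocol. The section a trainer would naturally work from gives the weaker one: from session 3 onward, the only contact it offers depends on the patient having a question. The section that justifies the risk rating assumes scheduled supervision by professionals.

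Three things are at stake.

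- **Patient protection.** The sessions are vigorous intervals done at home by people awaiting allogeneic transplant. Scheduled video is one of the stated ways of limiting that risk.
- **Compliance.** Section 7.5 says audits check conduct against the approved protocol. A missed monthly video would breach Section 7 yet comply with Section 4.1.1.
- **Definition of the intervention.** Section 7.0 says the study is meant to inform a randomized phase 2 trial. How much supervision belongs to the intervention should be stated once and consistently.

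**Working it through.** The plan gives no figure on this point, so there is none to reproduce. The check has two parts: set the texts side by side, then count the contacts that differ.

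**Side by side**

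| Session | Section 4.1.1 | Section 7.0 |
|---|---|---|
| 1 | In person | In person, monitored |
| 2 (first at home) | Videoconference | Monitored video link |
| Later, month 1 | Independent; staff reachable for questions | Monitored video once a week; otherwise not specified |
| Later, after month 1 | Independent; staff reachable for questions | Monitored video once a month to the end of the study, plus on request |

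The rows agree for sessions 1 and 2 and differ from session 3 on. Because the Section 7 schedule appears twice, it is not a stray phrase.

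**Contacts that Section 4.1.1 would leave out**

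These counts assume that every scheduled video is missed, that a month is 30 days, and that month 1 has four weekly contacts.

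Contacts omitted = weekly contacts in month 1 + floor((days − 30)/30)

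- Weekly contacts: 4 − 1 = 3 if the first home video counts as week 1, otherwise 4.
- Monthly contacts: about one for each further month.

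The length of training is not stated, so the windows below are assumptions built from figures in the documents:

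- **Short, 30 days.** The low end of the "2-3 month window between new patient evaluation and HCT" (60 days) less the longest wait for the assessment day, since patients "will return within one month (preferably within two weeks) for a separate day of assessments": 60 − 30 = 30.
- **Median.** Section 7.0 gives 101 days for the period before transplant. If that runs from the new patient evaluation, a 30- or 14-day wait leaves 101 − 30 = 71 or 101 − 14 = 87 days.
- **Outer limit, 180 days.** Section 3.1 admits patients whose transplant is planned within six months, taken here with no wait.

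| Window (days) | Month 1 | Later | Omitted per patient |
|---|---|---|---|
| 30 | 3–4 | floor(0/30) = 0 | 3–4 |
| 71 | 3–4 | floor(41/30) = 1 | 4–5 |
| 87 | 3–4 | floor(57/30) = 1 | 4–5 |
| 101 | 3–4 | floor(71/30) = 2 | 5–6 |
| 180 | 3–4 | floor(150/30) = 5 | 8–9 |

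If the monthly contacts continue after transplant, they add about 90/30 = 3 by discharge (about day 90), or 365/30 ≈ 12 by Year 1.

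**Share of sessions directly supervised in the first four weeks**

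At the maximum of three a week there are 3 × 4 = 12 sessions. Section 4.1.1 gives 2 in person or by video, 2/12 = 17%. Section 7.0 gives 1 + 4 = 5, or 6 if the first home video is extra: 5/12 = 42% to 6/12 = 50%. This assumes each video contact coincides with a training session.

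**The case against.** The strongest reply is that the texts can be read together. Section 4.1.1 gives the general pattern and Section 7.0 adds a specific schedule on top. Even under Section 7.0 most sessions are done alone, and Section 4.1.1 does not say that video stops. Section 4.0 already expects video to be used with exercise sessions. Recruitment is from one transplant program and the first session is at one named center, so a team that knows the whole protocol may never drop the calls.

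Part of this stands. The harm is conditional, and nothing in the documents shows staff working from Section 4.1.1 alone. But Section 4.1.1 makes no exception for scheduled video and no reference to Section 7, and Section 4.0 gives no frequency. The combined reading has to be supplied by the reader.

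Three stronger readings are tempting, and the documents do not support them.

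- **That later home sessions would be unmonitored.** Section 4.0 describes real-time tracker data with staff follow-up. Section 7.0 provides weekly or monthly assessment of intervention-related adverse events and staff reachable at all hours. Exercise-test clearance and the coronary exclusions apply under both texts. The adverse-event assessments may or may not be the same contacts as the video; the protocol does not say.
- **That a large fixed number of contacts would be lost.** Multiplying 3 to 9 by the 30 patients expected to train gives 90 to 270. That is a worst case in which everyone misses everything, on assumed windows and before transplant only. It is not an expected loss.
- **That the completion endpoint is undermined.** The documents give no basis for saying how video contact affects completion, and the rate can be interpreted under either rule.

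**Conclusion.** The inconsistency is real and should be corrected. It concerns a safety procedure, and it is more than missing detail because two stated rules differ from session 3 onward. Its size, if every scheduled video were omitted, is about 3 to 4 contacts per patient in the first month and about one a month afterwards. The monthly part has no firm upper limit because the end of training is not stated. The video is one of several safeguards, so the low-risk rating loses one of its stated supports and not all of them. No sample size, endpoint definition or analysis changes.

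The wording comparison needs no assumption. The counts rest on a 30-day month, four weekly contacts in month 1, and complete omission.

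**What to change.** Replace the quoted sentence in Section 4.1.1 with one that carries the Section 7 schedule, for example: *Monitored video sessions take place once a week during month one, once a month from then until the study ends, and whenever staff or the patient ask for one; the patient does all other sessions independently, with study staff reachable by iPad/iPhone.*

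Do not settle the conflict the other way, by deleting the video schedule from Section 7.0. That would remove a stated protection, and the weekly or monthly adverse-event assessments may depend on the same contacts.

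The cost is a one-sentence amendment, which Section 10.4 requires the IRB to approve before use. It needs no staff time or equipment beyond what Section 7.0 already commits to.

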4.1.2 Musclesound

Assessment of intramuscular adipose tissue (IMAT) and Intramuscular Glycogen Content (IMGC). IMGC and IMAT can be determined by ultrasound in different musclegroup throughout the body ,using MuscleSound® ultrasound technology. MuscleSound® ultrasound technology assessments of IMGC and IMAT have been validated against muscle-biopsies and CT/MRI imaging. Longitudinal and transverse ultrasound images of the m. rectus femoris, vastus lateralis, m. intercostalis / m. pectoralis, (head) m. temporalis, and/or (head) styloglossus. Complex grayscale analysis of the images was used to calculate the IMAT and IMGC; In addition, muscle thickness/Area and subcutaneous fat layer thickness (with grayscale analyses) are also assessed by ultrasound.

4.1.3 Body Composition Measures

Participants will have body composition assessed at the Duke Center for Living. To determine lean and fat mass changes participants will be assessed using air-displacement plethysmography (ADP). Briefly the BodPod machine is an ADP machine which uses whole-body densitometry to determine body composition (fat vs. lean). The machine uses very precise scales and volume displacement by sitting still inside the machine. The machine produces small volume changes inside the chamber and measures pressure responses to these changes. In total, each participant is inside the machine for no more than 5 minutes and accuracy is within 2% of that of dual-energy x-ray absorptiometry (DXA). Additionally, ADP has significantly fewer limitations than DXA, such as the weight of the participant, radiation exposure, cost and ease of use. In addition to ADP measurements, we will also measure waist and hip circumferences.

A Research Program Targeting Pre-, Peri-, and Post-transplant Optimization Program (R-POP)

An alternative body composition measure if BodPod is unavailable is bioelectrical impedance spectroscopy (BIS) via a bioimpedance analysis (BIA) device. BIA equipment does not measure muscle mass directly, but instead derives an estimate of muscle mass based on whole-body electrical conductivity. Skeletal muscle has a large amount of water, and segmental BIS can separately assess intracellular water (ICW) and extracellular water (ECW), which are divided by the muscle cell membrane. Segmental BIS can distinguish ICW and ECW from the total water in a particular segment. Segmental BIS is advantageous for assessments of a localized (left/right) region (arm, leg and trunk) instead of only the whole-body ICW reflects muscle cell mass, whereas ECW represents the sum of interstitial fluid and blood plasma in extracellular space. The calculations of ICW and ECW are only affected by segmental volume, so the ECW/ICW ratio could indicate the ratio of non-contractile tissue to contractile tissue regardless of assessed somatotype (age, gender, disease state). InBody S10 will be the BIS device used to obtain BIA. InBody is a FDA approved device, and DUH-approved used in Standard of Care.

